The individuals from OHSU are clinicians on the current study. However, all hard copies of data and coordination for the study will take place at NU. All recruitment will come from NU and then participants will be assigned to one of the clinicians. Enrollment decisions will be made by the team at NU. We are using these clinicians because they are experts in treating individuals with primary progressive aphasia, which is rare in the speech pathology field. If individuals are referred from OHSU, the NU team will complete all screening procedures to determine eligibility for the study.

The researchers joining us from OHSU ([name], M.S., CCC-SLP, speech-pathologist) who will be seeing patients is a Co-Investigator on the study. [name] (Co-Investigator) on the study will also be covered by this IAA. She will not see patients for the study, but is a part of the study team who will have access to participant data. [name]'s interactions with participants, and [name]'s data access for this study will be overseen by the Northwestern IRB. An IAA between Northwestern University and OHSU has been established between the two universities IRBs.

STUDY TIMELINES:

Participant participation in this study will last 1 year.

90 participants are intended to be enrolled over 5 years.

STUDY ENDPOINTS:

The primary endpoint of being able to discern differences between the treatment groups will occur when all 90 participants complete the research protocol. We intend to have the majority of patients (80/90) to have completed the interventions by the end of year 4.

PROCEDURES INVOLVED:

Study Design. Up to 100 participants will be randomized, 60% to the experimental group and 40% to the control group. The rationale for using an unequal enrollment design is to maximize the number of observations in the Experimental group for individuals with PPA, which may allow for further refinement and may mitigate study drop-out rates. Randomization will be blocked and stratified by subtype (PPA-L, PPA-G, PPA-S). Within each subtype, blocks will maintain the 60%:40% split of experimental:control, respectively.

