- **Experimental Group.** Individuals in the experimental group will receive a person-centered intervention. A person-centered intervention includes a combination of therapy approaches to maximize functional communication and life participation. This intervention will include, but not be limited to, impairment-based strategies, compensatory strategies, communication partner training, and disease education. Communication partners will be required to attend all evaluation and therapy sessions over the course of the study.
- Control Group. Individuals in the control group will receive impairment-based treatment that will target areas of weakness in a rehabilitation approach to improve function of a specific cognitive domain. They will receive disease-education at the first treatment session. Communication partners will attend the first treatment session and a portion of subsequent therapy sessions.

Study Procedures

All evaluations and therapy sessions will take place over a HIPAA compliant videoconferencing program. All sessions will be video-recorded through this program.

Orientation and Training:

Participants and communication partners will undergo an orientation to the technological aspects of the study over two one-hour sessions. At the initial orientation, participants will be consented to the study, complete demographic questionnaires, and if randomized to the experimental group, they will be instructed on how to fill out the brainstorming form for their personally relevant words that will be targeted in therapy. After this session, the participant and communication partner will work on the brainstorming form while the research coordinator assembles and mails the participant laptop computer with a webcam and Ethernet plug, technology guides, and self-report questionnaires. Participants and communication partners are asked to complete their brainstorming form in a 3-week time period and return it to the study team.

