Post-Intervention Evaluation 2: This evaluation will be identical to the **Post-Intervention Evaluation 1** in Block 1. This evaluation will take place approximately one week following the 5 weekly therapy sessions of Intervention Block 2. Identical to other evaluations, this will occur over two sessions lasting no more than 2 hours per session (4 hours in total).

12- month Evaluation: Approximately one year after the Baseline Evaluation, the participant will take part in a final evaluation. Post-treatment outcomes will be measured through standardized evaluation measures, communication participation measures, and language performance measures that have been given throughout the course of the study. Identical to other evaluations, this will occur over two sessions lasting no more than 2 hours per session (4 hours in total).

Scheduling Compliance:

Sessions: To successfully complete the trial, participants must complete 10 visits within 12 weeks for the first treatment block and 5 visits within 7 weeks for the second treatment block. Circumstances may arise that require the re-scheduling of visits. When this occurs, the following rules apply:

- No more than 2 visits may be scheduled within a 5-day window
- Sessions on consecutive days should be avoided

Visits that cannot be scheduled within these rules will be considered 'missed' visits. In the case of a missed visit, the visit will not be re-scheduled. Dosing effects resulting from missed visits will be accounted for in the statistical analyses. Participants with more than 2 missed visits will be asked if they would like to continue to receive the intervention as part of routine clinical care; however, the participant will be withdrawn from the study analysis.

6-Month and 12-Month Evaluations: These evaluations should be scheduled within a time window that includes the 2-weeks prior to or following the actual 6 or 12 month follow-up date.

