Aim 1: Determine the within-group response of the Experimental and Control treatments for adults with PPA. Aim 1a will provide a descriptive and quantitative characterization of the response to treatment including within- group effect sizes.

Statistical analysis Aim 1a: The primary analysis goals for Aim 1a will be (i) the estimation of the within-person change and the variability in this change along with the statistical significance of the change within each treatment group and (ii) the estimation of the within-group effect size for each treatment group. These analyses will be done for all outcomes.

Power calculation for Aim 1: In preliminary data, the Pearson correlation between the initial and 6 month CCRSA was 0.70. Assuming a standard deviation of σ for an outcome at one time, and assuming a correlation of 0.50 between the initial and 12 month measure (since follow-up is longer), then the standard deviation of the change is also σ . Similar assumptions will be made for all outcomes. The Experimental group with a sample size of 51 would have 80% power to detect a mean change that is 0.4 σ while the Control group with a sample size of 34 would have 80% power to detect a mean change of 0.5 σ . For testing correlations between the change in an outcome and a continuous measure, the Experimental group (n=51) would have 80% power to detect a correlation of 0.38 while the Control group (n=34) would have 80% power to detect a correlation of 0.46. Two-tailed tests and a Type I error rate of 5% are assumed for all calculations for Aim 1.

Aim 2: Determine if a person-centered dynamic treatment approach (Experimental) for adults with PPA will show more favorable communication participation outcomes as compared to an impairment-only treatment approach (Control) over a 12-month course of disease.

Specific Aim 2 Analysis: The group statistical analysis will focus on two participation measures (CCRSA, Goal Attainment Scaling [GAS]) and two language performance measures (% target word accuracy and % script accuracy). All outcomes are continuous measures except for GAS which is ordinal. The primary analyses will focus on the initial and 12-month time points. Secondary analyses will be done using all time points, specifying certain post-hoc comparisons of interest (e.g. comparing the effect of the preand post-evaluations for the 6-month Treatment Sessions between groups).

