Power Calculation for Aim 2: Power will be based on a sample size of 51 in the Experimental arm and 34 in the Control arm. For all language and participation outcomes, preliminary data were used to estimate unadjusted standard deviations (SDs). It is expected that analysis of covariance would reduce the unadjusted SDs but since longitudinal data were not available on all measures, the conservative approach will be to use the unadjusted SDs in the power calculation. The Table below gives the between-group effect size (in units of the scale) detectable with 80% power for each outcome measure using a two-tailed test and a Type I error rate of 0.017. For example, for the CCRSA scale, there is 80% power to detect an Experimental minus Control difference of 12% in the 12-month mean adjusted by analysis of covariance for the initial evaluation CCRSA level.

Measure	Туре	SD	Between-group effect size with n=51 and 34 per arm ^A
Lexical Retrieval	Language	19 16	13
Script Performance	Language	14 25	10
Confidence Rating Scale for Aphasia (CCRSA)	Participation	16 16	12
Goal Attainment Scaling (T-Score)	Participation	10 26	7
^A 80% power, 2-tailed p<0.025 for language measures and $p<0.017$ for participation measures			

Table 1. Power Calculations

All members of the study team will be trained on the procedures of how data are stored and managed. Members of the study team that are approved by the Northwestern IRB will have access to the REDcap database and to the web-application database. All access to these applications will be provided over encrypted-TLS communication and all servers are locked and managed in a physically secure facility with Marlok identity management. All data will be de-identified and stored as much.

All data will be checked by a research assistant who is different from the individual who administered the tests. This checking will take place on hard copies of outcome measures and data stored in REDcap. Discrepancies between raters will be recorded by a crossing out of original score and initialing the new score with the checkers initials. REDcap includes a feature where data can be marked as "unchecked" or "checked". Once data are checked by a second scorer, they will be marked as "checked" in REDcap.

Participants will be asked if they are willing to share data from the study with other researchers within the CNADC. If so, researchers will not receive any identifiable information.

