PROVISIONS TO MONITOR THE DATA TO ENSURE THE SAFETY OF PARTICIPANTS:

A data safety and monitoring board (DSMB) has been established for the proposed study. The members of this committee are not associated with the research project and work independently of the PI. They are all qualified to review the patient safety data generated by this study because of their unique expertise in the areas of statistics, speech-language therapy, primary progressive aphasia, dementia, treatment efficacy/outcomes and clinical trials. The committee will meet at least annually to review study data concerning recruitment, randomization, retention, compliance form completion, gender and minority inclusion, intervention effects and safety. The committee will be available at any time to advise on these issues.

At each meeting the committee will vote whether to continue the trial. Reasons for early termination of the study may include concerns about safety of the intervention or an early convincing beneficial effect of intervention. The committee may also recommend amendments to the study protocol if it appears that such are necessary for safety of scientific validity of the trial. Committee minutes will be part of annual Institutional Review Board review.

WITHDRAWAL OF PARTICIPANTS:

Participants can be withdrawn from the study for the following reasons: 1) Lost contact; 2) Missed visits due to: a) "no show" without rescheduling for two treatment sessions; or b) not adhering to scheduling compliance rules (see above); 3) Obtaining outside speech-language therapy during the study.

If individuals are withdrawn from the study, they will be sent a FedEx Airbill to send their laptop computer provided by the study back to Northwestern. They will be informed of the reasons why they were withdrawn. These reasons for possible withdrawal will be clearly stated in the consent form.

Data collected up until the point of lost contact with the participant will be used in analyses for the study.

RISKS TO PARTICIPANTS:

The risks for participation in the proposed research are minimal. Potential adverse events associated with this research include:

- 1. Loss of confidentiality
- 2. Fatigue and/or frustration in performing the online intervention
- 3. Depression and Anxiety: Caregivers of individuals with PPA and living with PPA can both be psychologically taxing experiences. It is not abnormal for individuals in these

Version Date: 04/16/2018

Page 12 of 18 HRP-593 / v011017

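### Withdrawal for obtaining outside speech-language therapy probably costs the 12-month outcome, which can bias the Aim 2 comparison if it is related to outcome and to arm

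*Combined protocol and SAP*

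**What the plan says.** WITHDRAWAL OF PARTICIPANTS lists three grounds on which a participant can be withdrawn: lost contact, missed visits, and "3) Obtaining outside speech-language therapy during the study". On withdrawal, "they will be sent a FedEx Airbill to send their laptop computer provided by the study back to Northwestern". No evaluation after withdrawal is described. On data, the section says only: "Data collected up until the point of lost contact with the participant will be used in analyses for the study".

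Under Specific Aim 2 Analysis, "The primary analyses will focus on the initial and 12-month time points"; analyses of all time points are secondary. The Power Calculation for Aim 2 describes the CCRSA comparison as one of 12-month means adjusted by analysis of covariance for the initial level. STUDY TIMELINES gives the follow-up: "Participant participation in this study will last 1 year".

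The arms differ in content (PROCEDURES INVOLVED). Experimental participants receive a combination of approaches, with the communication partner at every session. Controls receive impairment-based treatment, and "Communication partners will attend the first treatment session and a portion of subsequent therapy sessions".

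The documents contain no intention-to-treat statement, missing-data method, sensitivity analysis or expected dropout rate, and do not say how outside therapy is to be handled in the analysis.

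**The concern.** Obtaining outside therapy happens after randomisation and may depend on how the participant is doing and on what the assigned arm provides. Someone who has attended every study session can still meet this ground, so it is separate from the attendance rules. There is time for it to occur: the two treatment blocks must fit within windows of 12 and 7 weeks, which leaves about 52 - 19 = 33 weeks of the year without scheduled study therapy, in a progressive disease.

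If such participants leave before month 12 and no 12-month value is obtained, the primary comparison is made among those who remain. Keeping their earlier data helps the secondary all-time-point analyses. It does not supply the 12-month value that the primary analysis needs. If controls who are faring poorly leave more often, the remaining controls look better than their arm and an experimental advantage is understated. If the pattern is reversed, it is overstated. As written, the plan could neither measure nor correct either case.

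**Working it through.** **1. The plan's own figure.** Inputs from the Power Calculation for Aim 2 and Table 1: n = 51 and 34, CCRSA SD 16 (the second 16 in that table cell is read as a reference number), two-tailed alpha 0.017, power 80%.

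- Normal approximation: 16 × √(1/51 + 1/34) × (2.387 + 0.842) = 16 × 0.2214 × 3.228 = 11.4 points.
- Noncentral t: 11.6 points.

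The stated 12 is reproduced to the whole point. At exactly 12 points, power by the t version is 82.7%.

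**2. Bias from comparing only those retained.** In one arm, let p be the share withdrawn on this ground without a 12-month value, and d the retained-minus-withdrawn gap in mean 12-month CCRSA. Here d refers to the score that would have been observed at month 12, including any effect of the outside therapy.

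- Full-arm mean = retained mean - p × d, so the retained mean exceeds the full-arm mean by p × d.
- Bias in Experimental minus Control = pE × dE - pC × dC, which is (pE - pC) × d if the gap is the same in both arms.

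The documents give neither p nor d. The values below are assumptions; 16 points is one unadjusted SD from Table 1 and 8 points is half of that.

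| pE / pC | d = 8 | d = 16 |
|---|---|---|
| 5% / 5% | 0 | 0 |
| 5% / 10% | -0.4 | -0.8 |
| 5% / 15% | -0.8 | -1.6 |
| 5% / 20% | -1.2 | -2.4 |
| 5% / 25% | -1.6 | -3.2 |

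The largest entry is 3.2/12 = 27% of the detectable difference. The sign reverses if those withdrawn would have scored better, or if more are withdrawn from the experimental arm.

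**3. Baseline adjustment.** Analysis of covariance removes the part of the gap that the initial CCRSA explains. With the 0.50 correlation between initial and 12-month values assumed in the Aim 1 power calculation, the residual SD is 16 × √(1 - 0.25) = 13.9. A gap of one residual SD at 5%/25% then gives 0.20 × 13.9 = 2.8 points rather than 3.2.

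**4. Precision.** Taking the losses off 51 and 34, power at 12 points is 80.4% at 5%/5%, 77.1% at 5%/15% and 73.2% at 5%/25%. At 5%/25% the expected loss is 0.05 × 51 + 0.25 × 34 = 2.55 + 8.5, about 11 people. Intended enrolment of 90 exceeds 85 by 5, and the ceiling of 100 exceeds it by 15. Extra recruitment can restore precision but does not remove bias.

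**The case against.** The strongest reply is that much of this is inference. The rule says participants can be withdrawn, so it need not apply to everyone who seeks outside therapy. Laptop return does not rule out a later remote visit, since screening was done on participants' own computers. Differential uptake is speculative: the arms are dose-matched, and the background says people with PPA may not live near an experienced therapist, which would limit outside therapy in both arms. With equal rates and equal gaps the bias is zero. The rule may also be there to protect the treatment contrast. Keeping users of outside therapy in the analysis answers a different question, and if more controls use it and benefit, the difference shrinks.

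Most of this stands, and it limits the claim. A reader might infer that the protocol forbids evaluation after withdrawal, that everyone who seeks outside therapy is removed, that controls will be lost more often, or that a bias against the experimental arm has been shown. The documents support none of these: they describe no follow-up but do not exclude it, the rule is discretionary, and no rate is given for either arm. A reader might also infer that the rule must be deleted. That is a decision about participant management, and the statistical problem can be solved without it.

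The objection does not remove the gap. Wishing to protect the contrast is a reason to define how outside therapy enters the analysis and to record it. Dilution can be examined when the 12-month values exist; a value that was never collected cannot be recovered.

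**Conclusion.** The point holds in a limited form. Followed as written, the plan permits selection on a post-randomisation event before the primary time point, and names no method to deal with it. That is more than a missing detail, but bias is possible rather than shown. It requires that withdrawal on this ground costs the 12-month value, that those withdrawn differ in outcome from those retained, and that the rate or the gap differs by arm. Under the assumed ranges the effect on the CCRSA difference is 0 to about 3.2 points against 12, in either direction, and less after baseline adjustment to the extent that baseline explains the gap. The change is worth making because it is cheap and because the data cannot be obtained afterwards.

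**What to change.** Separate leaving study treatment from leaving follow-up. Whether study treatment continues is for the sponsor to decide. Whatever is decided:

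- State that participants who obtain outside speech-language therapy are still invited to the remaining remote evaluations, including month 12, and are analysed in the arm to which they were randomised.
- Record outside therapy at each evaluation (start date, type, number of sessions) and report it by arm.
- Add a sensitivity analysis that treats values after the start of outside therapy as missing, using a named method such as a likelihood-based repeated-measures model or multiple imputation. Its missing-data assumption should be stated, because a complete-case version would bring back the same selection.
- Reconcile the two statements on whose data are used. Scheduling Compliance says that after more than two missed visits "the participant will be withdrawn from the study analysis", while WITHDRAWAL OF PARTICIPANTS, which also covers missed visits, keeps data up to lost contact. That phrase does not clearly cover a withdrawn participant who is still in contact.

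The cost is a few protocol sentences, one data-collection form, and already planned remote evaluations for a few more people. The downside is some dilution of the contrast by outside therapy, which the records by arm and the sensitivity analysis allow the team to examine.
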